7.1.5.6 Safety Follow-Up Telephone call

All subjects who have either completed the trial or discontinued from the trial will have a safety follow-up phone call approximately 3 months after the last dose of trial medication.

7.2 Assessing and Recording Adverse Experiences

An adverse event is defined as any untoward medical occurrence in a patient or clinical investigation subject administered a pharmaceutical product and which does not necessarily have to have a causal relationship with this treatment. An adverse event can therefore be any unfavourable and unintended sign (including an abnormal laboratory finding, for example), symptom, or disease temporally associated with the use of a medicinal product or protocol-specified procedure, whether or not considered related to the medicinal product or protocol-specified procedure. Any worsening (i.e., any clinically significant adverse change in frequency and/or intensity) of a preexisting condition that is temporally associated with the use of the Sponsor's product, is also an adverse event.

Changes resulting from normal growth and development that do not vary significantly in frequency or severity from expected levels are not to be considered adverse events. Examples of this may include, but are not limited to, teething, typical crying in infants and children and onset of menses or menopause occurring at a physiologically appropriate time.

Sponsor's product includes any pharmaceutical product, biological product, device, diagnostic agent or protocol-specified procedure, whether investigational (including placebo or active comparator medication) or marketed, manufactured by, licensed by, provided by or distributed by the Sponsor for human use.

Adverse events may occur during clinical trials, or as prescribed in clinical practice, from overdose (whether accidental or intentional), from abuse and from withdrawal.

All adverse events that occur after the consent form is signed but before treatment allocation/randomization must be reported by the investigator if they cause the subject to be excluded from the trial, or are the result of a protocol-specified intervention, including but not limited to washout or discontinuation of usual therapy, diet, placebo treatment or a procedure. From the time of treatment allocation/randomization through 90 days following cessation of treatment, all adverse events must be reported by the investigator. Such events will be recorded at each examination on the Adverse Event case report forms/worksheets. The reporting timeframe for adverse events meeting any serious criteria is described in section 7.2.3.1. The investigator will make every attempt to follow all subjects with non-serious adverse events for outcome.

Electronic reporting procedures can be found in the Electronic Data Capture (EDC) data entry guidelines. Paper reporting procedures can be found in the Investigator Trial File Binder (or equivalent).

7.2.1 Definition of an Overdose for This Protocol and Reporting of Overdose to the Sponsor

In this trial, an overdose is any dose higher than the dose specified in Section 5.2 of this protocol.

If an adverse event(s) is associated with (“results from”) the overdose of Sponsor's product or vaccine, the adverse event(s) is reported as a non-serious adverse event, unless other serious criteria are met.

If a dose of Sponsor's product or vaccine meeting the protocol definition of overdose is taken without any associated clinical symptoms or abnormal laboratory results, the overdose is reported as a non-serious adverse event using the terminology “accidental or intentional overdose without adverse effect.”

All reports of overdose with and without an adverse event must be reported by the investigator within 24 hours to the Sponsor either by electronic media or paper. Electronic reporting procedures can be found in the EDC data entry guidelines. Paper reporting procedures can be found in the Investigator Trial File Binder (or equivalent).

7.2.2 Reporting of Pregnancy and Lactation to the Sponsor

Although pregnancy and lactation are not considered adverse events, it is the responsibility of investigators or their designees to report any pregnancy or lactation in a subject (spontaneously reported to them), including the pregnancy of a male subject's female partner that occurs during the trial.

Pregnancies and lactations of subjects and female partners of male subjects from the time the consent form is signed but before treatment allocation/randomization must be reported by the investigator if they cause the subject to be excluded from the trial, or are the result of a protocol-specified intervention, including but not limited to washout or discontinuation of usual therapy, diet, placebo treatment or a procedure. Pregnancies and lactations of subjects and female partners of male subjects that occur from the time of treatment allocation/randomization through 6 months following cessation of Sponsor's product must be reported. All reported pregnancies must be followed to the completion/termination of the pregnancy. Pregnancy outcomes of spontaneous abortion, missed abortion, benign hydatidiform mole, blighted ovum, fetal death, intrauterine death, miscarriage and stillbirth must be reported as serious events (Important Medical Events). If the pregnancy continues to term, the outcome (health of infant) must also be reported.

Such events must be reported within 24 hours to the Sponsor either by electronic media or paper. Electronic reporting procedures can be found in the EDC data entry guidelines. Paper reporting procedures can be found in the Investigator Trial File Binder (or equivalent).

7.2.3 Immediate Reporting of Adverse Events to the Sponsor

7.2.3.1 Serious Adverse Events

A serious adverse event is any adverse event occurring at any dose or during any use of Sponsor's product that:

- Results in death;
- Is life threatening;
- Results in persistent or significant disability/incapacity;
- Results in or prolongs an existing inpatient hospitalization;
- Is a congenital anomaly/birth defect;
- Is an other important medical event.

Note: In addition to the above criteria, adverse events meeting either of the below criteria, although not serious per ICH definition, are reportable to the Sponsor in the same timeframe as SAEs to meet certain local requirements.

- Is a cancer;
- Is associated with an overdose.

Refer to [Table 3](#) for additional details regarding each of the above criteria.

For the time period beginning when the consent form is signed until treatment allocation/randomization, any serious adverse event, or follow up to a serious adverse event, including death due to any cause, that occurs to any subject must be reported within 24 hours to the Sponsor if it causes the subject to be excluded from the trial, or is the result of a protocol-specified intervention, including but not limited to washout or discontinuation of usual therapy, diet, placebo treatment or a procedure.

For the time period beginning at treatment allocation/randomization through 90 days following cessation of treatment, any serious adverse event, or follow up to a serious adverse event, including death due to any cause, whether or not related to the Sponsor's product, must be reported within 24 hours to the Sponsor either by electronic media or paper. Electronic reporting procedures can be found in the EDC data entry guidelines. Paper reporting procedures can be found in the Investigator Trial File Binder (or equivalent).

Additionally, any serious adverse event, considered by an investigator who is a qualified physician to be related to the Sponsor's product that is brought to the attention of the investigator at any time outside of the time period specified in the previous paragraph also must be reported immediately to the Sponsor.

All subjects with serious adverse events must be followed up for outcome.

7.2.3.2 Events of Clinical Interest

Selected non-serious and serious adverse events are also known as Events of Clinical Interest (ECI) and must be reported to the Sponsor.

For the time period beginning when the consent form is signed until treatment allocation/randomization, any ECI, or follow up to an ECI, that occurs to any subject must be reported within 24 hours to the Sponsor if it causes the subject to be excluded from the trial, or is the result of a protocol-specified intervention, including but not limited to washout or discontinuation of usual therapy, diet, placebo treatment or a procedure.

For the time period beginning at treatment allocation/randomization through 90 days following cessation of treatment, any ECI, or follow up to an ECI, whether or not related to the Sponsor's product, must be reported within 24 hours to the Sponsor, either by electronic media or paper. Electronic reporting procedures can be found in the EDC data entry guidelines. Paper reporting procedures can be found in the Investigator Trial File Binder (or equivalent).

Events of clinical interest for this trial include:

1. an elevated AST or ALT lab value that is greater than or equal to 3X the upper limit of normal and an elevated total bilirubin lab value that is greater than or equal to 2X the upper limit of normal and, at the same time, an alkaline phosphatase lab value that is less than 2X the upper limit of normal, as determined by way of protocol-specified laboratory testing or unscheduled laboratory testing.*

*Note: These criteria are based upon available regulatory guidance documents. The purpose of the criteria is to specify a threshold of abnormal hepatic tests that may require an additional evaluation for an underlying etiology. The trial site guidance for assessment and follow up of these criteria can be found in the Investigator Trial File Binder (or equivalent).

2. Clinically significant opportunistic infections and TB.
3. Clinically significant hypersensitivity reactions.

7.2.4 Evaluating Adverse Events

An investigator who is a qualified physician will evaluate all adverse events with respect to the elements outlined in [Table 3](#). The investigator's assessment of causality is required for each adverse event. Refer to [Table 3](#) for instructions in evaluating adverse events.

Table 3 Evaluating Adverse Events

Maximum Intensity	Mild	awareness of sign or symptom, but easily tolerated (for pediatric trials, awareness of symptom, but easily tolerated)
	Moderate	discomfort enough to cause interference with usual activity (for pediatric trials, definitely acting like something is wrong)
	Severe	incapacitating with inability to work or do usual activity (for pediatric trials, extremely distressed or unable to do usual activities)
Seriousness	A serious adverse event (AE) is any adverse event occurring at any dose or during any use of Sponsor's product that:	
	† Results in death ; or	
	† Is life threatening ; or places the subject, in the view of the investigator, at immediate risk of death from the event as it occurred [Note: This does not include an adverse event that, had it occurred in a more severe form, might have caused death.]; or	
	† Results in a persistent or significant disability/incapacity (substantial disruption of one's ability to conduct normal life functions); or	
	† Results in or prolongs an existing inpatient hospitalization (hospitalization is defined as an inpatient admission, regardless of length of stay, even if the hospitalization is a precautionary measure for continued observation. (Note: Hospitalization for an elective procedure to treat a pre-existing condition that has not worsened is not a serious adverse event. A pre-existing condition is a clinical condition that is diagnosed prior to the use of a Merck product and is documented in the patient's medical history.); or	
	† Is a congenital anomaly/birth defect (in offspring of subject taking the product regardless of time to diagnosis); or	
	Is a cancer (although not serious per ICH definition, is reportable to the Sponsor within 24 hours to meet certain local requirements); or	
	Overdose, although not serious per ICH definition, whether accidental or intentional, with or without an accompanying adverse event/serious adverse event, is reportable to the Sponsor within 24 hours to meet certain local requirements.	
Other important medical events that may not result in death, not be life threatening, or not require hospitalization may be considered a serious adverse event when, based upon appropriate medical judgment, the event may jeopardize the subject and may require medical or surgical intervention to prevent one of the outcomes listed previously (designated above by a †).		
Duration	Record the start and stop dates of the adverse event. If less than 1 day, indicate the appropriate length of time and units	
Action taken	Did the adverse event cause the Sponsor's product to be discontinued?	
Relationship to Sponsor's Product	Did the Sponsor's product cause the adverse event? The determination of the likelihood that the Sponsor's product caused the adverse event will be provided by an investigator who is a qualified physician. The investigator's signed/dated initials on the source document or worksheet that supports the causality noted on the AE form, ensures that a medically qualified assessment of causality was done. This initialed document must be retained for the required regulatory time frame. The criteria below are intended as reference guidelines to assist the investigator in assessing the likelihood of a relationship between the test drug and the adverse event based upon the available information	
	The following components are to be used to assess the relationship between the Sponsor's product and the AE; the greater the correlation with the components and their respective elements (in number and/or intensity), the more likely the Sponsor's product caused the adverse event:	
	Exposure	Is there evidence that the subject was actually exposed to the Sponsor's product such as: reliable history, acceptable compliance assessment (pill count, diary, etc.), expected pharmacologic effect, or measurement of drug/metabolite in bodily specimen?
	Time Course	Did the AE follow in a reasonable temporal sequence from administration of the Sponsor's product? Is the time of onset of the AE compatible with a drug-induced effect (applies to trials with investigational medicinal product)?
	Likely Cause	Is the AE not reasonably explained by another etiology such as underlying disease, other drug(s)/vaccine(s), or other host or environmental factors
Relationship to Sponsor's Product (continued)	The following components are to be used to assess the relationship between the Sponsor's product and the AE: (continued)	
	Dechallenge	Was the Sponsor's product discontinued or dose/exposure/frequency reduced? If yes, did the AE resolve or improve? If yes, this is a positive dechallenge. If no, this is a negative dechallenge. (Note: This criterion is not applicable if: (1) the AE resulted in death or permanent disability; (2) the AE resolved/improved despite continuation of the Sponsor's product; (3) the trial is a single-dose drug trial; or (4) Sponsor's product(s) is/are only used one time.)

	Rechallenge	
Was the subject re-exposed to the Sponsor's product in this trial? If yes, did the AE recur or worsen? If yes, this is a positive rechallenge. If no, this is a negative rechallenge. (Note: This criterion is not applicable if: (1) the initial AE resulted in death or permanent disability, or (2) the trial is a single-dose drug trial; or (3) Sponsor's product(s) is/are used only one time.) NOTE: IF A RECHALLENGE IS PLANNED FOR AN ADVERSE EVENT WHICH WAS SERIOUS AND WHICH MAY HAVE BEEN CAUSED BY THE SPONSOR'S PRODUCT, OR IF RE-EXPOSURE TO THE SPONSOR'S PRODUCT POSES ADDITIONAL POTENTIAL SIGNIFICANT RISK TO THE SUBJECT THEN THE RECHALLENGE MUST BE APPROVED IN ADVANCE BY THE SPONSOR CLINICAL DIRECTOR AND THE INSTITUTIONAL REVIEW BOARD/INDEPENDENT ETHICS COMMITTEE.

	Consistency with Trial Treatment Profile	
Is the clinical/pathological presentation of the AE consistent with previous knowledge regarding the Sponsor's product or drug class pharmacology or toxicology?

The assessment of relationship will be reported on the case report forms /worksheets by an investigator who is a qualified physician according to his/her best clinical judgment, including consideration of the above elements.
		
Record one of the following:	Use the following scale of criteria as guidance (not all criteria must be present to be indicative of a Sponsor's product relationship).	
Yes, there is a reasonable possibility of Sponsor's product relationship.	
There is evidence of exposure to the Sponsor's product. The temporal sequence of the AE onset relative to the administration of the Sponsor's product is reasonable. The AE is more likely explained by the Sponsor's product than by another cause.
	
No, there is not a reasonable possibility of Sponsor's product relationship	
Subject did not receive the Sponsor's product OR temporal sequence of the AE onset relative to administration of the Sponsor's product is not reasonable OR the AE is more likely explained by another cause than the Sponsor's product. (Also entered for a subject with overdose without an associated AE.)
	

7.2.5 Sponsor Responsibility for Reporting Adverse Events

All Adverse Events will be reported to regulatory authorities, IRB/IECs and investigators in accordance with all applicable global laws and regulations, i.e., per ICH Topic E6 (R1) Guidelines for Good Clinical Practice.

7.3 TRIAL GOVERNANCE AND OVERSIGHT

7.3.1 Scientific Advisory Committee

This trial was developed in collaboration with a Scientific Advisory Committee (SAC). The SAC comprises both Sponsor and non-Sponsor scientific experts who provide input with respect to trial design, interpretation of trial results and subsequent peer-reviewed scientific publications.

8.0 STATISTICAL ANALYSIS PLAN

This section outlines the statistical analysis strategy and procedures for the study. Changes to analyses made after the protocol has been finalized, but prior to unblinding, will be documented in a supplemental SAP (sSAP) and referenced in the Clinical Study Report (CSR) for the study. Post hoc exploratory analyses will be clearly identified in the CSR.

8.1 Statistical Analysis Plan Summary

Key elements of the statistical analysis plan are summarized below; the comprehensive plan is provided in Sections 8.2-8.12.

Study Design Overview	Phase IV, randomized, double-blind withdrawal study to evaluate the efficacy and safety of golimumab (MK-8259, GLM) after treatment withdrawal, compared with continuous treatment (either full- or reduced-treatment regimen), in subjects with nr-axSpA
Treatment Assignment	In Period 1, all subjects receive open-label GLM. In Period 2, subjects who attained inactive disease status (at both Month 7 and Month 10 of open-label golimumab treatment) in Period 1 undergo stratified randomization, in a 1:1:1 ratio (Placebo QM : GLM QM : GLM Q2M).
Analysis Populations	Efficacy : The primary efficacy population is: subjects who are randomized in Period 2 and take at least one dose of trial medication in Period 2. Safety : All Subjects as Treated (ASaT).
Primary Endpoint(s)	Proportion of subjects without a “flare” during up to 12 months in Period 2.
Key Secondary Endpoints	None
Statistical Methods for Key Efficacy Analyses	The primary hypothesis will be evaluated by comparing treatment withdrawal (PBO) versus continued treatment with either GLM QM or GLM Q2M in the proportion of subjects without a “flare”, using a stratified Miettinen and Nurminen (M&N) test.
Statistical Methods for Safety Analyses	Percentages of subjects with AEs in Period 2 will be summarized, using 95% CIs based on the M&N method, for broad AE categories (subjects with: Any AE, a Drug-related AE, a Serious AE, an AE that is both Drug-related and Serious, and Discontinuation due to AE).
Interim Analyses	No interim analysis is planned.

Multiplicity	The Type-I error rate over the multiple treatment comparisons will be controlled by a sequential (step down) testing procedure.
Sample Size and Power	Approximately 300 subjects will be enrolled to yield approximately 114 subjects eligible for randomization in Period 2 of the study, assuming the proportion of subjects with inactive disease in Period 1 at both Months 7 and 10 is about 38% in GLM-treated subjects (based on study P07642). Using a randomization ratio of 1:1:1 into the PBO, GLM QM, and GLM Q2M arms, there will be 38 subjects in each treatment arm. Based on the results of prior studies, the proportion without “flare” during the 12 months following randomization is expected to be approximately 80% in subjects on continued monthly GLM and 30% in subjects in the treatment withdrawal (PBO) arm. Under these assumptions, the power to detect a difference between treatment withdrawal (PBO) and continued GLM treatment (QM or Q2M) in the proportions of subjects without a “flare” exceeds 99%, given $\alpha=0.05$ (2-sided). As the “flare” rates may differ from those observed in prior studies, the targeted sample sizes of 38 subjects per arm will provide 88% power to detect differences of 75% vs. 40% in the continued GLM (QM or Q2M) vs. PBO treatment arms.

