8.8 Multiplicity

The Type-I error rate over the multiple treatment comparisons will be controlled by a sequential (step down) testing procedure. Testing of the primary hypotheses will begin with comparison of the GLM QM versus PBO. The GLM Q2M versus PBO comparison will be performed only if the primary efficacy GLM QM versus PBO analysis is statistically significant at two-sided $\alpha = 0.05$.

All other efficacy analyses will be considered supportive and/or exploratory.

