8.9 Sample Size and Power Calculations

A total of approximately 300 subjects will be enrolled. Assuming the proportion of subjects who attain inactive disease in Period 1 at both Months 7 and 10 is about 38% (based on the GO-AHEAD study, P07642 [1]), 300 enrolled subjects would result in approximately 114 subjects eligible for Period 2 of the study. With 114 subjects randomized in a ratio of 1:1:1 into the PBO, GLM QM, and GLM Q2M arms, 38 subjects are expected in each treatment arm.

Based on an expected proportion who do not “flare” of 80% in the GLM QM arm (based on study P07642) and 30% in the PBO arm (based on studies of subjects with early axial spondyloarthritis [7]), the power to detect a difference between treatment withdrawal (PBO) vs. continued treatment with GLM QM in the proportion of subjects who do not “flare” exceeds 99%, given $\alpha=0.05$ (2-sided). (See the bold text in Table 6 below.) If the primary hypothesis is rejected for the GLM QM vs. PBO (treatment withdrawal) comparison, then tests of GLM Q2M vs. PBO will be conducted. It is not known if the proportion who do not “flare” for the GLM Q2M arm will be similar to that for the GLM QM arm; but with a sample size of 38 per arm, the study will have 88% power to detect differences of 75% vs. 40% in the proportions of subjects who do not “flare”, should the estimates of absence of “flare” differ from what has been observed in prior studies [7]. (See the bold italic text in [Table 7](#) provides estimates of power for several response scenarios.

Table 7 Power for the Primary Endpoint, Comparing Two Treatment Arms

Treatment withdrawal: Placebo arm	Continued golimumab: QM or Q2M arm	
Proportion who Do not “flare” (N=38)	Proportion who Do not “flare” (N=38)	Power†
20%	80%	99%
	75%	99%
	70%	99%
	65%	98%
	60%	96%
30%	80%	99%
	75%	98%
	70%	95%
	65%	87%
	60%	75%
40%	80%	96%
	75%	88%
	70%	75%
	65%	59%
	60%	41%
†Assumes $\alpha=0.05$ and 2-sided test QM=every month; Q2M=every 2 months		

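### The 88% power given for every-2-months golimumab ignores the step-down: with both regimens at 75% and placebo at 40% flare-free, the planned procedure gives it about 81%

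*Combined protocol and SAP*

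**What the plan says.** Section 8.1 (Sample Size and Power) plans 114 randomized subjects in a 1:1:1 ratio, so that "there will be 38 subjects in each treatment arm". The expected flare-free proportions are "approximately 80% in subjects on continued monthly GLM and 30% in subjects in the treatment withdrawal (PBO) arm". On that basis it claims power above 99% for continued golimumab, naming both QM and Q2M. It then says that the same sample size "will provide 88% power to detect differences of 75% vs. 40% in the continued GLM (QM or Q2M) vs. PBO treatment arms".

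Section 8.9 limits the claim of more than 99% to QM against placebo. It says that Q2M will be tested if the QM comparison succeeds, and continues: "It is not known if the proportion who do not “flare” for the GLM Q2M arm will be similar" to that of QM. The same sentence then offers reassurance: "with a sample size of 38 per arm, the study will have 88% power to detect differences of 75% vs. 40"%. Table 7 is titled "Power for the Primary Endpoint, Comparing Two Treatment Arms", carries the footnote "Assumes $\alpha=0.05$ and 2-sided test", and heads its golimumab column as the QM or Q2M arm.

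Section 8.8 sets the order of testing: "The GLM Q2M versus PBO comparison will be performed only if the primary efficacy GLM QM versus PBO analysis is statistically significant" at two-sided 0.05. No section gives the power for Q2M under that order.

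**The concern.** Under a fixed sequence, the second hypothesis can be rejected only if the first has been. The power for Q2M is therefore the probability that both comparisons are significant. That cannot exceed the pairwise power of either test, and it falls clearly below when QM has an appreciable chance of failing. The plan nevertheless gives one pairwise figure for both regimens, and in Section 8.9 gives it at the point where Q2M is being discussed.

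There is a second mismatch. The base case in Section 8.1 supplies a flare-free rate for monthly golimumab only, yet the power above 99% is claimed for Q2M as well. Section 8.9 declines to assume a Q2M rate.

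Q2M against placebo is one of only two comparisons under Type I error control, and the only confirmatory test of the reduced regimen. If it fails, readers will judge the result against the stated 88%. That figure describes a Q2M test carried out on its own, which this trial does not plan.

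**Working it through.** **Inputs.** n = 38 per arm and the rates 75%, 40%, 80% and 30% come from Sections 8.1 and 8.9; two-sided α = 0.05 from Table 7; the testing order from Section 8.8; the Miettinen and Nurminen (M&N) test from Section 8.6.1. The Q2M rate is not given in the plan, so a range is shown.

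**Step 1: reproduce the plan's 88%.** The usual two-proportion formula, with pooled variance under the null, is

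Power = Φ{[δ√n − z√(2p̄(1−p̄))] / √(p₀(1−p₀) + p₁(1−p₁))}

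With p₀ = 0.40, p₁ = 0.75, δ = 0.35, p̄ = 0.575 and z = 1.96:

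- δ√n = 0.35 × 6.164 = 2.158
- z√(2 × 0.575 × 0.425) = 1.96 × 0.699 = 1.370
- √(0.24 + 0.1875) = 0.654
- Power = Φ(0.787 / 0.654) = Φ(1.204) = 0.886

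Exact binomial enumeration of the unstratified M&N test gives 0.884. The formula reproduces all 15 rows of Table 7 to within about 1 point. The stated figures are therefore sound as pairwise powers.

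**Step 2: apply the step-down.** Given the placebo count x, the two golimumab arms are independent, so

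P(both significant) = Σₓ P(placebo count = x) × P(QM significant | x) × P(Q2M significant | x)

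Exact M&N enumeration with n = 38 per arm gives:

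| QM | Q2M | Placebo | Q2M pairwise, exact | Table 7 | Q2M under step-down |
|---|---|---|---|---|---|
| 75% | 75% | 40% | 88.4% | 88% | about 81% (0.8105) |
| 80% | 75% | 40% | 88.4% | 88% | 86.2% |
| 70% | 75% | 40% | 88.4% | 88% | 71.3% |
| 75% | 70% | 40% | 76.1% | 75% | 71.3% |
| 70% | 70% | 40% | 76.1% | 75% | 63.8% |
| 80% | 80% | 30% | 99.6% | 99% | 99.3% |
| 80% | 65% | 30% | 88.0% | 87% | 87.9% |
| 80% | 60% | 30% | 76.1% | 75% | 76.1% |

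**Step 3: cross-checks for 75/75/40.** The shared placebo arm gives the two test statistics a correlation of about 0.24 / (0.24 + 0.1875) = 0.561. A bivariate normal calculation with that correlation gives 0.815. A simulation of 400,000 trials with the stratified M&N test, assuming CRP strata of 23 and 15 per arm, gives 0.811. Multiplying the two powers as if independent (0.8857 × 0.8857 = 0.784) is too pessimistic, because it ignores the shared arm.

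**Step 4: could 88% be the conditional power?** No. Given that QM is significant, Q2M power is 0.8105 / 0.8844 = 0.916. So 88% is neither the step-down power nor the conditional power for Q2M.

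**The case against.** The strongest reply is that nothing has been miscalculated. Table 7 reproduces, its title says that it compares two arms, and Sections 8.8 and 8.9 both state the testing order. Reporting power per comparison beside a fixed sequence is common, and nowhere does the plan call the 88% a joint power. All of that stands: the figure is misapplied, not wrong in itself.

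The second reply is that the step-down costs almost nothing if QM performs as planned. With QM at 80% and placebo at 30%, the loss for Q2M is at most 0.3 points at each Q2M rate from 60% to 80%. The drop to 81% needs both placebo at 40% and QM at 75%; with QM kept at 80% the loss is about 2 points. This also stands, and it limits the reach of the point. But 75% against 40% is the scenario that the plan itself chose to show robustness, and there it names Q2M.

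The third reply is that Section 8.9 already limits the claim of more than 99% to QM, and that 99.3% would be right if Q2M matched QM. That is so, but Section 8.1 attaches the claim to Q2M without stating that condition. With QM at 80%, placebo at 30% and Q2M at 60%, the figure would be 76%.

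**Conclusion.** The concern holds. For 75% against 40%, the stated 88% is the power for QM. For Q2M under the planned sequence it is about 81% when both regimens are at 75%, a loss of about 7 points. Holding Q2M at 75% and placebo at 40%, it ranges from 71% to 86% as QM moves from 70% to 80%. These figures assume 38 analysed subjects per arm and two-sided 0.05; the table uses the unstratified M&N test, and the stratified simulation agrees for 75/75/40.

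The consequence is limited to the stated power of the second test, mainly in the less favourable scenarios. QM power, Type I error control and the planned analysis are unaffected, and the base case is essentially unchanged at 99.3% if Q2M is also at 80%. The power statements should be corrected, but the design need not be.

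**What to change.** In Sections 8.1 and 8.9 and in Table 7, label the existing figures as pairwise power, applicable as they stand to QM against placebo. Add a Q2M column with power under the step-down, stating the assumed QM rate: for example 81% for 75/75/40 and 86% for 80/75/40 (QM/Q2M/placebo). In Section 8.1, either limit the claim of more than 99% to QM or state the Q2M rate that it assumes.

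This is a text and table edit, and its only cost is a slightly less favourable stated figure. No change in sample size is requested. For reference, 88% step-down power at 75/75/40 would take about 46 per arm.
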